3.10 Subject/Study Discontinuation

3.10.1 Screen Failures

A screen failure is defined as subject from whom informed consent is obtained, but

- Inclusion/Exclusion criteria are not met, or
- Subject was unable to be randomized, or
- Subject withdrew consent prior to randomization/surgical intervention.

3.10.2 Subject Discontinuation

Subjects may end their participation in the study at any time for any reason(s). The reason for discontinuation should be documented.

Early termination will be defined as any post-randomization study termination prior to completion of the Month 12 assessment. Subjects that terminate early will not be replaced. Reasons for early termination will be tabulated by center as well as by the study overall.

Subjects that have not completed the study and who are unable to be contacted or for whom the reason for discontinuation is unknown will be considered "lost to follow-up". The site will make three attempts to contact the subject by either telephone, certified mail or by an alternative method. The site may continue to try to achieve appropriate follow-up until the 12 month follow-up visit . Because these follow-ups typically only require the collection of pain assessments, Quality of Life assessments, Daily Pain Medication Diary, and Daily Pain Diary, the assessments may be captured via phone or returned to the site electronically or by mail.

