3.5 Study Endpoints

3.5.1 Safety Endpoints

Primary Safety Endpoint

- 1. The rate of occurrence of Serious Adverse Events (SAEs) at 3 months
- 2. The rate of occurrence of Adverse Experiences (AEs) or Unanticipated Adverse Device Effects at 3 months

Secondary Safety Endpoints

1. The rate of occurrence of SAEs, AEs and/or UADEs at 6, 9 and 12 months

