Visit 3 (Week 2) is a safety visit and the following will be performed.

- 1. Obtain relevant vital signs (height / weight)
- 2. Post-Operative Care
- 3. Wound Assessment (safety check remove sutures, wound check, etc.)
- 4. Pain Assessments (VAS, PROMIS®)
- 5. Concomitant Medication review and Daily Pain Medication Diary review (treatments including quantity and class of pain medications, review with subject and re-educate if needed, dispense new diary)
- 6. Daily Pain Diary (review with subject, re-educate if needed, dispense new diary)
- 7. Adverse events review

3.9.4 Visits 4: Months 1

The following will be performed at Visits 4:

- 1. Obtain relevant vital signs (height / weight)
- 2. Wound Assessment
- 3. Pain Assessments (VAS, PROMIS®)
- 4. Quality of Life Questionnaires (FHSQ
- Concomitant Medication review and Daily Pain Medication Diary review (treatments
 including quantity and class of pain medications, review with subject and re-educate if
 needed, dispense new diary)
- 7. Daily Pain Diary (review with subject, re-educate if needed)
- 8. Adverse Events review

3.9.5 Visits 5-7: Months 3, 6, 9

The following will be performed at Visits 5 through 7:

- 1. Obtain relevant vital signs (height / weight)
- 2. Pain Assessments (VAS, PROMIS®)
- 3. Quality of Life Questionnaires (FHSQ
- Concomitant Medication review and Daily Pain Medication Diary review (treatments
 including quantity and class of pain medications, review with subject and re-educate if
 needed, dispense new diary)
- 6. Daily Pain Diary (review with subject, re-educate if needed)
- 7. Adverse Events review

3.9.6 Visit 8: End of Study/Early Termination Visit, Month 12

The following will be performed at Visit 8/End of Study/Early Termination:

- 1. Obtain relevant vital signs (height / weight)
- 2. Wound Assessment
- 3. Pain Assessments (VAS, PROMIS®)
- Quality of Life Questionnaires (FHSQ
- 6. Concomitant Medication review and Daily Pain Medication Diary review (treatments including quantity and class of pain medications, review with subject)
- 7. Daily Pain Diary (review with subject)
- 8. Adverse Events review

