4.5 Adverse Event Reporting Procedures

The Investigator is responsible for recording and reporting all Adverse Events observed or reported during the study, regardless of their relationship to the study product or their clinical significance. Subjects will be instructed to contact the site Investigator at any time if symptoms develop. The adverse event reporting window will begin at the time the subject signs the informed consent form and will continue throughout the study and up to 30 days following the End of Study visit. The Investigator is required to completely document all adverse events in detail in the subject's medical record (source documents) and report the event on the Adverse event CRF. Whenever possible, the AE will be

recorded using standard medical terminology in order to avoid the use of vague, ambiguous, or colloquial expressions.

Concurrent illnesses that are present at or before study device administration, which manifest with the same severity, frequency, or duration subsequent to study device administration, need not be recorded as AEs. Similarly, signs or symptoms related to a pre-existing disease (prior to patient consenting) need not be recorded as AEs and will be recorded in the medical history CRF. However, medical history events that increase in severity or duration must be reported on the AE CRF.

Each AE must be promptly recorded and sufficiently documented by the Investigator or a qualified designee, even if the AE is assessed by the Investigator as unrelated to therapy with study device. The Investigator or qualified designee should attempt, if possible, to establish a diagnosis based on the presenting signs and symptoms. Each AE must also be described by date and time of onset, date and time of cessation, frequency (intermittent or continuous), the action taken (change in study device, concomitant medication, etc.), and outcome. In addition, the site Investigator must evaluate all AEs with respect to their severity and relationship to the study device according to the definitions given in the above tables 4-1 and 4-2.

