APPENDIX B: SCHEDULE OF ASSESSMENTS

Assessments	Visit 1 Screening Pre-operative	Visit 2 Operative Day 0 Operative	Visit 3 Week 2 Day 14 Post-Op	Visit 4 Week 4 Month 1 Day 30 Assessment	Visit 5 Week 12 Month 3 Day 90	Visit 6 Month 6 Day 180 Assessment	Visit 7 Month 9 Day 270 Assessment	Visit 8 Month 12 Day 360 EOS/ET
Informed Consent	X							
Inclusion/Exclusion Criteria	X	X						
Relevant Medical History	X							
Demographics	X							
Neuroma Information	X							
Relevant Vital Signs ¹	X	X	X	X	X	X	X	X
Operative Information		X						
Randomization ²		X						
Post-operative Care			X					
Wound Assessment			X	X	,			X
Pain Assessments ³	X	X	X	X	X	X	X	X
Quality of Life Questionnaires ⁴	X			X	X	X	X	X
Daily Pain Medication Diary and Concomitant Medication Log ⁵	X	X	X	X	X	X	X	X
Daily Pain Diary	X	X	X	X	X	X	X	X
Adverse Events		X	X	X	X	X	X	X
					I			

 $^{^{1}}$. Vital signs to include weight, Height will only be recorded one time at visit 1

² Comparative study only

^{3.} Pain Assessments: VAS and PROMIS® (for V2 Operative Day 0, VAS and PROMIS® performed prior to nerve block, and VAS performed again post

nerve block – ONLY if nerve block is performed during screening visit).

4. Quality of Life Questionnaires include: FHSQ

5. Daily Pain Medication Diary (including quantity, quality and class of pain medications) related to the nerve injury should be collected during Screening and Operative day and any changes/additions should be collected during the study.

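### The remote follow-up rule in Protocol 3.10.2 leaves out the adverse event review that the protocol requires at every post-operative visit, so adverse events may be under-ascertained in subjects followed by phone, mail or electronic return

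*Protocol*

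**What the plan says.** The rule stands in the lost-to-follow-up paragraph of Protocol 3.10.2, which concerns: "Subjects that have not completed the study and who are unable to be contacted or for whom the reason for discontinuation is unknown". The site makes three contact attempts and may keep trying until the 12-month visit. The paragraph then gives the reason for remote capture, "Because these follow-ups typically only require the collection of pain assessments, Quality of Life assessments, Daily Pain Medication Diary, and Daily Pain Diary", and the permission itself: "the assessments may be captured via phone or returned to the site electronically or by mail".

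The visit lists ask for more. Protocol 3.9.3 to 3.9.6 put an AE review on the list for Week 2, Month 1, Months 3, 6 and 9, and Month 12/Early Termination. The Month 12 entry reads "8. Adverse Events review". The schedule in Protocol Appendix B, repeated in SAP section 5, marks Visits 2 to 8: "Adverse Events X X X X X X X". No footnote exempts remote contacts.

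The primary safety endpoints are SAE and AE/UADE rates at 3 months. The secondary safety endpoint is "The rate of occurrence of SAEs, AEs and/or UADEs at 6, 9 and 12 months" (Protocol 3.5.1; SAP 9.3.1).

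**The concern.** The four items named in 3.10.2 supply efficacy and medication data. None of them asks about adverse events. A pack returned by post or electronically that holds only those items contains no AE question and involves no conversation in which an event could come up. The subject can thus contribute a VAS score for an interval in which nobody asked about safety.

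That subject still counts in the safety denominator, because SAP 7.4.4 includes everyone who received the device or underwent neurectomy. SAP 9.3 defines AE rates and summaries but has no category for an interval in which AEs were not assessed. SAP 7.3 imputes only the primary endpoint and analyses everything else on the data available. In a summary table, an interval in which nobody asked could look the same as one without events.

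At stake are the primary and secondary safety endpoints. Protocol 5.10 also makes the absence of a clinically significant difference in product-related AE rates part of study success, and missed events push towards that conclusion.

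**Working it through.** **1. The remote list against the visit requirements**

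| Item | Required at follow-up visits | In the 3.10.2 remote list |
|---|---|---|
| Pain assessments | Every post-operative visit | Yes |
| Quality of life | Month 1 onward | Yes |
| Pain medication diary, pain diary | Every post-operative visit | Yes |
| Adverse event review | Every post-operative visit | No |
| Concomitant medication review | Every post-operative visit | No |
| Wound assessment | Week 2, Month 1, Month 12 | No |

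The AE review is on all of the lists, so a description of what is typical does not account for leaving it out. The stated premise does not match the protocol's own schedule.

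**2. Whether another section fills the gap**

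- Protocol 4.5: "The Investigator is responsible for recording and reporting all Adverse Events observed or reported during the study". Subjects are also told to contact the site if symptoms develop. The duty covers events that reach the site. For a subject the site has had trouble reaching, that depends on spontaneous reporting.
- Protocol 4.1 requires AEs during or after implantation to be recorded. It gives no method for asking about them remotely.
- Protocol 3.4.4.3 asks for End of Study data before discontinuation. A subject already lost has usually passed that point.

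The general duty remains, but no section describes how AEs are solicited by phone, mail or electronic return.

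**3. Illustrative size**

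The documents state no AE rate, remote share or dropout rate, so there is no plan figure to reproduce. The arm size follows from SAP 7.1 and 7.2: 86 / 2 = 43. Everything else is assumed:

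- *p*, true proportion with an AE: 10–40%, taken as the same in remote and attending subjects
- *f*, share of subjects whose AEs would be found only through remote contact: 5–20%
- *m*, share of those AEs missed: 0 to 1

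Observed proportion = p × (1 − f × m). Subjects missed per arm = 43 × p × f × m.

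| p | f | Observed, m = 1 | Missed per arm, m = 1 |
|---|---|---|---|
| 10% | 5% | 9.5% | 43 × 0.10 × 0.05 = 0.22 |
| 20% | 10% | 18% | 43 × 0.20 × 0.10 = 0.86 |
| 20% | 20% | 16% | 43 × 0.20 × 0.20 = 1.72 |
| 40% | 20% | 32% | 43 × 0.40 × 0.20 = 3.44 |

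At m = 0 the loss is zero in every row. At m = 0.5 it is half the figure shown.

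**4. Effect on the comparison between arms**

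- Equal loss shrinks a real difference. With assumed true rates of 30% and 15% and 20% of events missed, 0.30 × 0.80 = 24% and 0.15 × 0.80 = 12%, so 15 points become 12.
- Unequal loss creates a false difference. With equal true rates, m = 1, and remote shares of 20% and 5%, the gap is p × (0.20 − 0.05): 1.5, 3.0 and 6.0 points at p = 10%, 20% and 40%. Nothing in the documents suggests that the remote share would differ between arms; this only shows how large the effect could be.

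**The case against.** A reader might infer that remotely followed subjects are never asked about AEs, that they are counted as having none, and that the reported rates are therefore too low. The documents do not support any of these.

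- Section 3.10.2 gives a reason why remote capture is acceptable. It does not waive the AE review, which stays in the visit lists and the schedule, and the duties in Protocol 4.1 and 4.5 still apply. A site may well ask by phone.
- SAP 7.4.4 says who is in the safety population. No section says an unassessed interval is coded as event-free. The SAP's introduction refers to case report forms and a data management plan for data-collection details. They are not available here, and the remote-contact form may carry an AE question.
- The rule sits in the lost-to-follow-up paragraph, so it does not plainly cover every missed visit. For the subjects it does cover, the likely alternative is no contact at all, so remote capture does not itself remove AE data.
- The results at m = 1 are a worst case for the assumed p and f. AE reviews on Day 0, Week 2 and Month 1 precede the 3-month visit, so a subject lost after Month 1 loses only later events.
- Protocol 5.10 concerns product-related AEs, whereas the illustration uses all AEs. SAP 9.3.2 plans summaries and listings, with no test between arms. That hard-to-reach subjects have more unreported events is plausible but not documented.

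These points limit the claim to a possible loss of unknown size. They do not remove the conflict: 3.10.2 describes the follow-ups as needing less than the schedule requires, and a site following it literally has no prompt to ask about AEs.

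**Conclusion.** The point holds as an internal conflict with a possible effect on safety ascertainment. Protocol 3.10.2 rests remote follow-up on a list that omits a review required at every post-operative visit. AE, SAE and UADE rates at 3, 6, 9 and 12 months may be understated as a result; the documents do not show that they will be.

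The size is unknown. Within the assumed ranges it lies between zero and about 3.4 subjects per arm of 43. The upper figure needs a 40% AE risk, a 20% remote share and every AE in those subjects missed. It also assumes equal risk in remote and attending subjects, which the documents neither support nor contradict.

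**What to change.** In Protocol 3.10.2:

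- Remove the statement that these contacts usually need just the four items.
- Add to the remote list an AE/SAE/UADE review covering the time since last contact, and a concomitant medication review.
- State that a remote contact without an AE review is recorded as *AE status not assessed*, and not as no AE.
- State that a wound assessment that cannot be done remotely is recorded as not done. An on-site visit for this purpose is not requested: it would add visits and work against the reason for remote capture.

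The cost is a short protocol edit and a few extra questions on the remote-contact form, with no added visits.

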3.10.3 Termination of the Study

Conditions that may warrant termination of the clinical study include, but are not limited to, the following:

- Discovery of an unexpected, serious, or unacceptable risk to subjects; or,
- Decision by the Sponsor to suspend or discontinue testing, evaluation, or development of the study product.

Conditions that may warrant termination of the clinical study at an investigative site include, but are not limited to, the following:

- The investigative site fails to comply with all applicable regulations;
- Deliberate submission of false information from the site to Axogen, Corp., their designee, or regulatory authorities;
- Inadequate adherence to protocol requirements; or
- Inadequate enrollment.

In the event of a discontinuation of the study at an investigative site, the Investigator will return all study materials including study documentation and CRFs to the Sponsor, provide a written statement explaining the reason for termination, and notify the appropriate Institutional Review Board/Ethics Committee.

4. ADVERSE EVENTS

4.1 Adverse Event Definitions

An adverse event (AE) is defined as any untoward event (including abnormal lab findings) experienced by a subject (whether or not considered product-related by the Investigator or Sponsor) after the patient consents to participate in the trial. All AEs that occur during or after study product implantation/device insertion must be recorded in the subject's medical record and reported on the adverse event CRF.

4.2 List of Anticipated Adverse Events

Consistent with the subject's informed consent form and the risk analysis section of this protocol, the following adverse events are known and may potentially occur during the subject's participation in this investigation:

- mild incisional redness;
- tenderness of surgical area;
- mild edema of surgical area;
- decreased pain at surgical area; and/or
- numbness

Severity of Adverse Events

Adverse events will be graded for severity and noted in the description of the event using the NCI (NIH)-developed Common Terminology Criteria for Adverse Events (NCI CTCAE), Version 5.0. In addition, any AE associated with subject termination from the study must be reported according to IRB requirements. The following severity grades (1-5) shown below in table 4-1 will be used in assessing adverse events using the CTCAE V5.0 as a guiding reference:

Table 4.3-1: Severity of Adverse Events

Grade	Description
Grade 1 (Mild)	Asymptomatic or mild symptoms; clinical diagnostic
98 9852 3	observations only; intervention not indicated

Grade 2 (Moderate)	Minimal, local or noninvasive intervention indicated; limiting age-appropriate instrumental ADL*
Grade 3 (Severe)	Medically significant but not immediately life-threatening; hospitalization or prolongation of hospitalization indicated; disabling; limiting self-care ADL**
Grade 4 (Life Threatening)	Life-threatening consequences; urgent intervention indicated
Grade 5 (Death)	Death related to AE

4.4 Relationship to Study Product or Control Procedure

The Investigator will assess the relationship of each adverse event to the study product and study procedure, using the criteria outlined in Table 4.4-1.

Table 4.4–1: Relationship of Adverse Events to Study Product or Control Procedure

Relationship	Description
Unrelated	An AE that is clearly and uncontrovertibly due to extraneous causes (disease,
	environment, etc) and does not meet the criteria for study device relationship listed
	under possible or probable.
Possible	An AE may be considered as possibly related if:
	1) it cannot be reasonably explained by the subject's clinical state or by
	environmental or toxic factors; or
	it follows a reasonable temporal sequence from administration of study device;
	or,
	3) it follows a known pattern of response to the study device.
Probable	An AE considered, with a high degree of certainty, to be related to the study
	device. An AE may be considered probably related to study device if:
	1) it cannot be reasonably explained by the known characteristics of the subject's
	clinical state or by environmental or toxic factors;
	and at least one of the following is true:
	2) it follows a reasonable temporal sequence from administration of study device;
	it follows a known pattern of response to study device;
	4) it disappears or decreases upon removal
Definitely	An AE that is clearly and uncontrovertibly due to study device.
Related	

4.5 Adverse Event Reporting Procedures

The Investigator is responsible for recording and reporting all Adverse Events observed or reported during the study, regardless of their relationship to the study product or their clinical significance. Subjects will be instructed to contact the site Investigator at any time if symptoms develop. The adverse event reporting window will begin at the time the subject signs the informed consent form and will continue throughout the study and up to 30 days following the End of Study visit. The Investigator is required to completely document all adverse events in detail in the subject's medical record (source documents) and report the event on the Adverse event CRF. Whenever possible, the AE will be

recorded using standard medical terminology in order to avoid the use of vague, ambiguous, or colloquial expressions.

Concurrent illnesses that are present at or before study device administration, which manifest with the same severity, frequency, or duration subsequent to study device administration, need not be recorded as AEs. Similarly, signs or symptoms related to a pre-existing disease (prior to patient consenting) need not be recorded as AEs and will be recorded in the medical history CRF. However, medical history events that increase in severity or duration must be reported on the AE CRF.

Each AE must be promptly recorded and sufficiently documented by the Investigator or a qualified designee, even if the AE is assessed by the Investigator as unrelated to therapy with study device. The Investigator or qualified designee should attempt, if possible, to establish a diagnosis based on the presenting signs and symptoms. Each AE must also be described by date and time of onset, date and time of cessation, frequency (intermittent or continuous), the action taken (change in study device, concomitant medication, etc.), and outcome. In addition, the site Investigator must evaluate all AEs with respect to their severity and relationship to the study device according to the definitions given in the above tables 4-1 and 4-2.

4.6 Serious Adverse Events

A Serious Adverse Event (SAE) is any untoward medical occurrence that occurs per the following definition:³⁹

- Results in death;
- Is immediately life threatening In the opinion of the site Investigator, the participant was at substantial risk of dying at the time of the event, or use or continued use of the device might have resulted in the death of the subject;
- Requires in-patient hospitalization or prolongation of existing hospitalization. Complications that occur during hospitalization are adverse events, and if a complication prolongs hospitalization, the event is considered serious. Emergency room visits that do not result in overnight hospital admissions should be evaluated for one of the other serious outcomes (e.g., life-threatening; required intervention to prevent permanent impairment or damage);
- Results in disability or Permanent Damage substantial disruption of a person's ability to conduct normal life functions, i.e., resulted in a significant, persistent or permanent change, impairment, damage or disruption in body function/structure, physical activities and/or quality of life;
- Results in a Congenital Anomaly/Birth Defect suspect that exposure to the device prior to conception or during pregnancy may have resulted in an adverse outcome in the child; or
- Requires Intervention to Prevent Permanent Impairment or Damage medical or surgical
 intervention was necessary to preclude permanent impairment of a body function, or prevent
 permanent damage to a body structure, either situation suspected to be due to the use of the
 device.
- Other Serious (Important Medical Events) when the event does not fit the other outcomes, but the event may jeopardize the subject and may require medical or surgical intervention

(treatment) to prevent one of the other outcomes. Examples include allergic brochospasm (a serious problem with breathing) requiring treatment in an emergency room, serious blood dyscrasias (blood disorders) or seizures/convulsions that do not result in hospitalization. The development of drug dependence or drug abuse would also be examples of important medical events.

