5.9 Safety Analyses

The safety endpoints will compare the nature and incidence of AEs between treatment groups. The safety objective is to show that there is no clinically significant difference of product-related adverse events between Axoguard® Nerve Cap and neurectomy study arms. Specifically, AEs, will be analyzed as a group and any change in the incidence rate of the listed AEs post treatment will be noted. AE nomenclature will be standardized according to the Medical Dictionary for Medical Activities (MedDRA)-preferred term and system organ classification. The occurrence of the treatment-emergent AEs (TEAEs) will be summarized by repair type using MedDRA preferred terms, system organ classifications, and severity. All AEs will be listed for individual subjects and summarized by verbatim and preferred terms. Separate summaries of treatment-emergent SAEs and AEs related to repair type will be generated.

Any event reported on the CRF that occurs on or after the treatment will be defined as treatmentemergent. Additionally, it is assumed that an AE, which was reported to have started on Day 0 without an associated onset time, may have occurred after the treatment. Hence, AEs occurring on Day 0 with no defined onset time will also be considered treatment-emergent.

Subject disposition will be presented for all subjects. The number of subjects who completed the study and discontinued from the study will be provided. The reasons for early discontinuation will also be presented.

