- Month 6 Visit: Month 3 Visit until Month 6 Visit
- Month 9 Visit: Month 6 Visit until Month 9 Visit
- Month 12 Visit: Month 9 Visit until Month 12 Visit

A subject is considered to have had a recurrence of symptomatic neuroma if all of the following conditions are met:

 Subject experiences a pain level greater than 1 on the 10-point scale of the daily pain diary at least one time during the assessment interval

- The average daily dose of morphine (mg/day) calculated using morphine equivalent dosing during the assessment interval is higher than the average daily dose during the baseline interval (between Screening visit and Operative Day 0)
- VAS pain score is higher at assessment visit than at baseline visit

Adverse Event

An AE is defined as any untoward event (including abnormal lab findings) experienced by a subject (whether or not considered product-related by the site Investigator or Sponsor) after the patient consents to participate in the trial. All AEs that occur during or after study product implantation/device insertion must be recorded in the subject's medical record and reported on the adverse event CRF.

Serious Adverse Events

A serious adverse event (SAE) is any untoward medical occurrence that occurs per the following definition.

- Results in death:
- Is immediately life threatening in the opinion of the site Investigator, the participant was at substantial risk of dying at the time of the event, or use or continued use of the device might have resulted in the death of the subject;
- Requires in-patient hospitalization or prolongation of existing hospitalization.
 Complications that occur during hospitalization are adverse events, and if a complication
 prolongs hospitalization, the event is considered serious. Emergency room visits that do
 not result in overnight hospital admissions should be evaluated for one of the other
 serious outcomes (e.g., life-threatening; required intervention to prevent permanent
 impairment or damage);
- Results in a Congenital Anomaly / Birth Defect suspect that exposure to the device prior to conception or during pregnancy may have resulted in an adverse outcome in the child; or
- Requires Intervention to Prevent Permanent Impairment or Damage medical or surgical
 intervention was necessary to preclude permanent impairment of a body function, or
 prevent permanent damage to a body structure, either situation suspected to be due to the
 use of the device.

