- Other Serious (Important Medical Events) when the event does not fit the other
 outcomes, but the event may jeopardize the subject and may require medical or surgical
 intervention (treatment) to prevent one of the other outcomes.

Unanticipated Adverse Device Effects

An unanticipated adverse device effect (UADE) is defined as any serious adverse effect on health or safety or any life-threatening problem or death caused by, or associated with, a device, if that effect, problem, or death was not previously identified in nature, severity, or degree of incidence in the Investigational Plan or application (including a supplementary plan or

application), or any other unanticipated serious problem associated with a device that relates to the rights, safety, or welfare of subjects.

Concomitant Medications

Concomitant medications are those medications taken after the procedure. This definition includes medications started prior to the procedure but continuing concomitantly afterward. Concomitant medications will be analyzed similarly to those reported in the Daily Pain Medication Diary utilizing MME dosing and MQS score conversions.

[figure not shown]
Previous Medications

Previous medications are those medications started and stopped prior to the procedure.

7. General Statistical Considerations

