9.3.2. Analyses

All AEs will be summarized by seriousness, relatedness to the treatment (as assessed by the participant's physician) and severity. All AEs will be listed for individual participants.

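### One SAE criterion requires suspected device causality and so cannot be met in the neurectomy arm; equal counting of SAEs then rests on a judgment-based catch-all (minor)

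*Protocol*

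**What the plan says.** Protocol 4.6 lists the outcomes that make an adverse event serious. One is an intervention needed to preclude permanent impairment or prevent "permanent damage to a body structure, either situation suspected to be due to the use of the" device. SAP section 6 repeats the condition in its own SAE definition: "prevent permanent damage to a body structure, either situation suspected to be due to the" use of the device.

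Two other lines matter here because they carry no device condition:

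- Hospitalization: "Requires in-patient hospitalization or prolongation of existing hospitalization".
- The catch-all: "Other Serious (Important Medical Events) when the event does not fit the other outcomes, but the event may jeopardize the subject". It goes on to events that may need treatment to prevent one of the other outcomes. The SAP keeps this line: "outcomes, but the event may jeopardize the subject and may require medical or surgical" intervention.

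The first primary safety endpoint in Protocol 3.5.1 is "The rate of occurrence of Serious Adverse Events (SAEs) at 3 months", and SAP 9.3.1 lists it as well. Protocol 5.9 states: "The safety endpoints will compare the nature and incidence of AEs between treatment groups". It also calls for a separate summary of treatment-emergent SAEs. For the analysis itself, SAP 9.3.2 says: "All AEs will be summarized by seriousness, relatedness to the treatment" and severity.

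**The concern.** Seriousness describes the outcome of an event, and causality is a separate judgment. When one seriousness criterion contains a causality condition that only one arm can satisfy, the two arms are not counted by the same rule.

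The event at issue is an intervention, without inpatient admission, to prevent lasting damage after foot nerve surgery. In the cap arm it has an explicit route to SAE status if the investigator suspects the device. In the neurectomy arm that route is closed. If control events are then classed as serious less often, equal true harm would appear as an SAE excess with the cap, and a true reduction in such interventions with the cap would be partly masked. Seriousness also triggers reporting to the sponsor within 24 hours (Protocol 4.6.1), so expedited surveillance is affected as well as the tables.

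**Working it through.** **No plan figure to reproduce.** The documents give no expected SAE rate, safety margin, safety test or safety power. The check is a reading of the criteria, followed by an illustration with assumed rates.

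**Step 1: which routes are open to each arm** (for an intervention to prevent permanent damage)

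| Criterion | Cap arm | Neurectomy arm |
|---|---|---|
| Intervention to prevent permanent impairment or damage | Open if the device is suspected | Closed: no device |
| Hospitalization or prolongation | Open | Open |
| Disability or permanent damage (Protocol 4.6) | Open if the damage occurs | Open if the damage occurs |
| Important medical events | Open, by judgment | Open, by judgment |

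Three details bear on how well the open routes work for controls.

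- Under hospitalization, both documents direct emergency room visits without overnight admission to the other serious outcomes. They give required intervention to prevent permanent impairment as an example, which is the criterion closed to controls.
- The disability or permanent-damage outcome is in Protocol 4.6 but does not appear in the SAP section 6 list as available for review.
- Protocol 3.7.1 states that the surgeon cannot be blinded, and neither document provides for blinded classification of seriousness.

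**Step 2: size under stated assumptions**

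Inputs: 86 randomized subjects at 1:1 (Protocol 3.1, SAP section 4), so n = 86 / 2 = 43 per arm. Both arms are in the safety population as SAP 7.4.4 defines it.

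Assumptions, none of them from the documents:

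- The true rate r of such interventions, not serious by any other route, is the same in both arms: 2%, 5%, 10% or 15%.
- Every cap-arm case is suspected to be due to the device.
- A share c of control cases is captured by the important-medical-events line.

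Expected SAEs from this source: cap = n × r; neurectomy = n × r × c.
Spurious excess in percentage points = 100 × r × (1 − c).

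| r | Cap, expected (43 × r) | Neurectomy, c = 0 | Neurectomy, c = 0.5 | Neurectomy, c = 1 | Excess in points at c = 0 / 0.5 / 1 |
|---|---|---|---|---|---|
| 2% | 0.86 | 0 | 0.43 | 0.86 | 2 / 1 / 0 |
| 5% | 2.15 | 0 | 1.08 | 2.15 | 5 / 2.5 / 0 |
| 10% | 4.30 | 0 | 2.15 | 4.30 | 10 / 5 / 0 |
| 15% | 6.45 | 0 | 3.23 | 6.45 | 15 / 7.5 / 0 |

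The second assumption makes these upper values. If only a share a of cap-arm cases is attributed to the device, and the rest go to the catch-all at the same capture c, the cap-arm expectation is n × r × [a + (1 − a) × c]. The excess is then 100 × r × a × (1 − c) points, smaller in proportion to a.

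**The case against.** The strongest reply is that the list already has a remedy. A control intervention that fails the device-conditional line fits no other outcome. It therefore falls to the important-medical-events line, which covers medical or surgical treatment given to prevent one of the other outcomes and has no device condition. Hospitalization is also arm-neutral. This stands, and it is why the range must start at zero. It does not remove the point, because that line turns on whether an event may jeopardize the subject, as judged by someone who knows the allocation. The Protocol's examples for it (bronchospasm, blood dyscrasias, seizures, drug dependence) are far from a local surgical re-intervention.

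A reader might go further and infer that the same re-intervention is automatically an SAE with the cap and never one after neurectomy, so that control events are lost and the primary safety test is biased. The documents do not support that reading:

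- The cap-arm route is not automatic. The investigator must suspect the device, which is also an unblinded judgment.
- Control events are not lost. Protocol 4.5 requires every adverse event to be recorded whatever its relationship to the product, the second primary safety endpoint covers AEs, and SAP 9.3.2 lists all AEs by participant. At most, such an event is classed as non-serious.
- There is no safety test to bias. SAP 9.3.2 plans summaries only, and the safety part of study success in Protocol 5.10 refers to product-related adverse event rates, not SAE counts. Significance levels for hypothetical SAE splits are therefore beside the point.

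**Conclusion.** The point holds as a minor one. One SAE criterion in both documents is tied to the device and cannot be met in the neurectomy arm. Whether a comparable control event is counted as serious then depends mainly on a judgment-based line applied by unblinded investigators, so the descriptive between-arm comparison of the primary SAE rate may under-count control events.

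The size cannot be established from the documents. With equal true rates of 2% to 15% and all cap-arm cases attributed to the device, the spurious excess runs from 0 points with full capture by the catch-all to 2 to 15 points with no capture. That is 0 to about 6 events among 43. The upper end needs three unfavorable assumptions together: a high rate, full attribution to the device and no control capture. The plan does not make such a distortion inevitable, but it does nothing to ensure that capture is equal.

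**What to change.** In Protocol 4.6 and SAP section 6, end the criterion after the reference to permanent damage to a body structure and strike the clause on suspected device causality. Seriousness then follows one rule in both arms. Causality stays in the relationship assessment (Protocol 4.4) and in the UADE definition (Protocol 4.7, repeated in SAP section 6), so no device information is lost.

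Widening the clause to cover the device or the study procedure would open the criterion to controls. It would still keep a causality judgment inside the seriousness definition, so deletion is cleaner.

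The cost is one clause in each document and a few more control-arm events that need 24-hour SAE reporting. Some cap-arm events not attributed to the device would also come in under this line. Every event that meets the present wording would still qualify.
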